5.5 Criteria for Taking a Participant Off Protocol Therapy

Duration of therapy will depend on individual response, evidence of disease progression and tolerance. In the absence of treatment delays due to adverse event(s), treatment may continue until one of the following criteria applies:

- Disease progression
- Intercurrent illness that prevents further administration of treatment
- Unacceptable adverse event(s)
- Participant demonstrates an inability or willingness to comply with the oral medication regimen and/or documentation requirements.
- Participant decides to withdraw from the protocol therapy.
- General or specific changes in the participant's condition render the participant unacceptable for further treatment in the judgement of the treating investigator.

Participants will be removed from the protocol therapy when any of these criteria apply. The reason for removal from protocol therapy, and the date the participant was removed, must be documented in the case report form (CRF). Alternative care options will be discussed with the participant.

When a participant is removed from protocol therapy and/or is off-treatment, on follow-up, or off-study, the relevant off-treatment/off-study information will be updated in OnCore

In the event of unusual or life-threatening complications, treating investigators must immediately notify the Overall PI, [name] at [contact] or [name].

5.6 Duration of Follow Up

Participant survival information will be collected, preferably via office visit or telephone contact, every 4 weeks (\pm 1 week) from the date of last dose of study drug until the participant's death or until the participant is lost to follow-up, or until study closure (approximately 6 months after the last participant terminates treatment). A participant will be determined to be lost to follow-up only after at least 3 attempts to contact him/her have been made over a 4-month period. At least two of these attempts to contact must be made through certified letters.

The following information will be collected:

- The participant's survival status, and if deceased, the date of death.
- The method by which the survival status was assessed and the date it was assessed.
- Any subsequent anti-cancer therapy received after discontinuation from study drug.

In addition, survival participants removed from study for unacceptable adverse events will be followed for resolution or stabilization of the adverse event.

5.7 Criteria for Taking a Participant Off Study

Participants will be removed from study when any of the following criteria apply:

- Lost to follow-up
- Withdrawal of consent for data submission
- Death

The reason for taking a participant off study, and the date the participant was removed, must be documented in the case report form (CRF). In addition, the study team will ensure Off Treatment/Off Study information is updated in OnCore in accordance with DF/HCC policy REGIST-101.

Participants that receive protocol therapy will not be replaced in this trial.

DOSING DELAYS/DOSE MODIFICATIONS

6.1 Criteria for dose delays/dose modifications

In general, participants experiencing **Grade 1 and 2** drug related toxicities should not have the dose of BVD-523 modified. However, appropriate supportive care should be provided for the management of drug related toxicities. Grade 2 toxicities may require dose or schedule modifications (delaying or omitting individual doses) due to potentially greater clinical significance; however, this should occur after discussion with Principal Investigator.

Dosing of BVD-523 must be delayed if a participant experiences a **Grade 3 non-hematologic** toxicity. If the toxicity resolves (returned to baseline or decreased to Grade \leq 1) within 14 days, dosing of BVD-523 may be resumed with a 25% dose reduction.

Exceptions to this rule are as follows:

- Grade 3 fatigue persistent for \leq 7 days
- Grade 3 nausea, vomiting, or diarrhea persisting \leq 72 hours with maximum supportive care
- Grade 3 electrolyte events if they are resolved with replacement within 24 hours
- Lymphopenia regardless of grade
- The following grade 3 laboratory abnormalities will not be considered dose limiting if they return to baseline within 7 days: elevated bilirubin, AST, ALT, cholesterol, amylase, lipase, creatinine and hypertriglyceridemia

Dosing of BVD-523 must be delayed if a participant experiences the following **Grade 2 hematologic** toxicities:

- thrombocytopenia ($< 50,000/\mu\text{L}$)
- neutropenia ($< 1,000/\mu\text{L}$) lasting > 7 days

Dosing of BVD-523 must be delayed if a participant experiences the following **Grade 3 hematologic** toxicities:

- hemoglobin decrease (< 8.0 g/dL)
- grade 3 or 4 febrile neutropenia (defined as temperature $\geq 101^\circ\text{F}$ with a neutrophil count $\leq 1,000$ cells/ μL).

If the toxicity resolves (returned to baseline or decreased to Grade \leq 1) within 14 days, dosing of BVD-523 may be resumed with a 25% dose reduction

In the case of **Grade 4 hematologic or non-hematologic** (except alopecia) toxicity, **or persistent Grade 3** toxicity despite one dose level reduction, the dose level will be reduced by a

total of 50 %. BVD-523 dose should not be reduced by more than 50 %. Participants unable to tolerate BVD-523 at a dose level of 50%, or whose drug related toxicity has not returned to baseline or Grade \leq 1 within 14 days, will be discontinued from study, unless clinical benefit has been demonstrated and a lower dose might, in the opinion of the PI, maintain clinical benefit.

Dose Level	BVD-523 Dose
-2	300mg, BID
-1	450mg, BID
0	600mg, BID

Nausea	Management/Next Dose for BVD-523
\leq Grade 1	No change in dose
Grade 2	Hold until \leq Grade 1. Resume at same dose level.
Grade 3	Hold* until $<$ Grade 2. Resume at one dose level lower, if indicated.**
Grade 4	Off protocol therapy
*Participants requiring a delay of $>$ 2 weeks should go off protocol therapy.	
**Participants requiring $>$ two dose reductions should go off protocol therapy.	
Recommended management: antiemetics.	

Diarrhea	Management/Next Dose for BVD-523
\leq Grade 1	No change in dose
Grade 2	Hold until \leq Grade 1. Resume at same dose level.
Grade 3	Hold* until $<$ Grade 2. Resume at one dose level lower, if indicated.**
Grade 4	Off protocol therapy
*Participants requiring a delay of $>$ 2 weeks should go off protocol therapy.	
**Participants requiring $>$ two dose reductions should go off protocol therapy.	
Recommended management: Loperamide antidiarrheal therapy	
Dosage schedule: 4 mg at first onset, followed by 2 mg with each loose motion until diarrhea-free for 12 hours (maximum dosage: 16 mg/24 hours)	
Adjunct anti-diarrheal therapy is permitted and should be recorded when used.	

Neutropenia	Management/Next Dose for BVD-523
\leq Grade 1	No change in dose
Grade 2	Hold until \leq Grade 1. Resume at same dose level.
Grade 3	Hold* until $<$ Grade 2. Resume at one dose level lower, if indicated.**
Grade 4	Off protocol therapy
*Participants requiring a delay of $>$ 2 weeks should go off protocol therapy.	
**Participants requiring $>$ two dose reductions should go off protocol therapy.	

Thrombocytopenia	Management/Next Dose for BVD-523
≤ Grade 1	No change in dose
Grade 2	Hold until ≤ Grade 1. Resume at same dose level.
Grade 3	Hold* until < Grade 2. Resume at one dose level lower, if indicated.**
Grade 4	Off protocol therapy
*Participants requiring a delay of >2 weeks should go off protocol therapy.	
**Participants requiring > two dose reductions should go off protocol therapy.	

Rash	Management/Next Dose for BVD-523
≤ Grade 1	No change in dose; topical antibiotics, steroids, and moisturizers indicated
Grade 2	No change in dose; Oral antibiotics indicated, oral steroids should be considered
Grade 3	Hold until ≤ Grade 1. Resume at same dose level. Oral antibiotics and steroids indicated
Grade 4	Hold until ≤ Grade 1. Resume at one dose level lower if indicated **
*Participants requiring a delay of >2 weeks should go off protocol therapy.	
**Participants requiring > two dose reductions should go off protocol therapy.	
Rash should be initially treated with topical steroids and topical clindamycin or doxycycline. If these do not sufficiently control the rash then would consider adding oral antibiotic therapy with doxycycline or minocycline. If rash is still not responding to therapy would consider adding a short course of oral steroids.	

ADVERSE EVENTS: LIST AND REPORTING REQUIREMENTS

All adverse events experienced by participants will be collected from the time of the first dose of study treatment, through the study and until the final study visit. Participants continuing to experience toxicity at the off-study visit may be contacted for additional assessments until the toxicity has resolved or is deemed irreversible.

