7.3 Adverse Event Characteristics

- **CTCAE term (AE description) and grade:** The descriptions and grading scales found in the revised NCI Common Terminology Criteria for Adverse Events (CTCAE) version 5.0 will be utilized for AE reporting. All appropriate treatment areas should have access to a copy of the CTCAE version 5.0. A copy of the CTCAE version 5.0 can be downloaded from the CTEP web site http://ctep.cancer.gov/protocolDevelopment/electronic_applications/ctc.htm.

- **For expedited reporting purposes only:**
 - AEs for the agent(s) that are listed above should be reported only if the adverse event varies in nature, intensity or frequency from the expected toxicity information which is provided.
 - Other AEs for the protocol that do not require expedited reporting are outlined in the next section (Expedited Adverse Event Reporting) under the sub-heading of Protocol-Specific Expedited Adverse Event Reporting Exclusions.

- **Attribution of the AE:**
 - Definite – The AE *is clearly related* to the study treatment.
 - Probable – The AE *is likely related* to the study treatment.
 - Possible – The AE *may be related* to the study treatment.
 - Unlikely – The AE *is doubtfully related* to the study treatment.
 - Unrelated – The AE *is clearly NOT related* to the study treatment.

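### Section 6.1 gives two unreconciled rules for neutropenia and thrombocytopenia below Grade 4, one by cell count and one by grade, and does not say which governs.

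*Combined protocol and SAP*

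**What the plan says.** All the dosing rules in question stand in section 6.1 of the protocol.

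- **Opening paragraph.** In general, participants with Grade 1 or 2 drug-related toxicity "should not have the dose of BVD-523 modified". The same paragraph then allows dose or schedule changes for Grade 2 events after discussion with the Principal Investigator.
- **Hematologic text.** A delay is mandatory if a participant "experiences the following Grade 2 hematologic toxicities". Two are listed, each by count: platelets below 50,000/µL, with no duration condition, and neutrophils below 1,000/µL, only if this lasts more than 7 days. A separate Grade 3 list follows (hemoglobin below 8.0 g/dL, and febrile neutropenia). After that second list comes the restart sentence: on resolution to baseline or Grade 1 or lower within 14 days, "dosing of BVD-523 may be resumed with a 25% dose reduction".
- **Neutropenia and thrombocytopenia tables.** These give no counts and no minimum duration. The Grade 2 row holds the drug and then reads "Grade 1. Resume at same dose level". The Grade 3 row holds the drug until below Grade 2 and restarts one level lower where indicated. A footnote marked on the Grade 3 row takes participants off therapy if the delay exceeds 2 weeks.
- **Dose levels.** 600 mg BID (level 0), 450 mg BID (level -1) and 300 mg BID (level -2).

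Section 7.3 names CTCAE version 5.0 for adverse event reporting and says "All appropriate treatment areas should have access to a copy of the CTCAE version 5.0". The grade cut-offs themselves are not printed anywhere in the documents.

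**The concern.** A site treating a participant with a low neutrophil or platelet count finds two instructions in one section. One is triggered by a count, the other by a grade, and they are linked only by a Grade 2 label that the documents give no means of checking. Nothing says whether the text or the table prevails.

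At stake are whether the drug is interrupted and at what dose it restarts. Section 9.0 has instructions for sites outside DFCI, so more than one team may be reading the section. Section 13.7 summarises study treatment by dose and cumulative dose. With at most 25 participants, a few handled differently could be visible in that summary, and the difference would reflect the reading of the protocol as well as tolerability.

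**Working it through.** **Inputs.** The starting dose, dose levels, counts, durations and restart wording are all from section 6.1. CTCAE cut-offs are not available, so both possible labels are carried through. Events are below Grade 4, the participant is on 600 mg BID, and the neutropenia cases are without fever, because febrile neutropenia has its own entry in the text.

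**Step 1. Do the text's percentages and the tables' levels use the same units?**

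- 600 × 0.75 = 450 mg, which is level -1.
- 600 × 0.50 = 300 mg, which is level -2.

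A 25% reduction from the starting dose is therefore exactly one dose level, and the two rules can be compared directly.

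**Step 2. The same event under each rule.**

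| Event | Hematologic text | Table, if Grade 2 | Table, if Grade 3 |
|---|---|---|---|
| Platelets <50,000/µL, any duration | Delay; restart at 450 mg BID* | Hold; restart at 600 mg BID | Hold; restart at 450 mg BID where indicated |
| Neutrophils <1,000/µL, >7 days | Delay; restart at 450 mg BID* | Hold; restart at 600 mg BID | Hold; restart at 450 mg BID where indicated |
| Neutrophils <1,000/µL, ≤7 days | No delay required | Hold; restart at 600 mg BID | Hold; restart at 450 mg BID where indicated |

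*If the restart sentence covers the Grade 2 list. If it covers only the Grade 3 list just above it, the text gives no restart dose for these events.

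**Step 3. What depends on the label.**

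- Rows 1 and 2: the restart doses differ only in the Grade 2 column. Daily dose is 2 × 450 = 900 mg against 2 × 600 = 1,200 mg, and (1,200 - 900)/1,200 = 25%. In the Grade 3 column both give 450 mg BID. What remains is a difference of wording: the table reduces only where indicated, while the text permits resumption at the reduced dose.
- Row 3: the mismatch is present in both columns. The table calls for a hold at once; the hematologic text requires none until the count has been low for more than 7 days.

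**Step 4. What agrees.** Neither the text nor the table sets a minimum duration for thrombocytopenia. The maximum delay also matches (14 days against 2 weeks), apart from the table marking it only on its Grade 3 row.

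**The case against.** The strongest reply is that little of this is an outright contradiction. If Grade 2 in the text is a slip for Grade 3, text and table restart at the same dose. If the 25% sentence belongs only to the Grade 3 list, the table supplies a restart dose where the text is silent. The text also says when a delay is compulsory without forbidding an earlier one, so a site that holds for a 5-day neutropenia breaches no hematologic rule. All three points are fair, and they limit the claim. They do not remove it: the first concedes that a mandatory dosing rule carries the wrong grade, the second relies on a reading the section does not state, and the third leaves a site that reads only the text free not to hold when the table says hold.

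Several stronger readings are tempting and should not be made.

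- **Three competing actions for one Grade 2 event.** The opening sentence is qualified as general, and its own paragraph allows Grade 2 changes after discussion with the Principal Investigator. Only two provisions compete.
- **An unconditional 450 against 600 mg conflict.** This needs both a literal Grade 2 label and a 25% sentence that reaches that list.
- **A duration mismatch for both cell types.** It applies to neutropenia only.
- **A bleeding-risk argument from the platelet cut-off.** The documents attach no such meaning to 50,000/µL.

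Grade 4 is a separate matter. There the text reduces by a total of 50% and the two tables take the participant off therapy. That too needs reconciling, but it is not part of this point.

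**Conclusion.** The point stands in a limited form. Below Grade 4, the hematologic text and the two tables in section 6.1 do not match, and no order of precedence is given.

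- **Independent of the label (Grade 2 or 3):** afebrile neutrophils below 1,000/µL for 7 days or less lead to no mandatory delay under the hematologic text and to a hold under the table.
- **Conditional:** restart at 450 or 600 mg BID, a 25% difference in daily dose, if the Grade 2 label is literal and the 25% sentence covers that list. If the counts are Grade 3, this difference largely disappears, and the error is then the label.

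The assessment assumes that the scale named in section 7.3 for reporting is also the one meant in section 6.1. How often these counts will occur is not given; the hematologic findings in section 7.2 are from animals. The effect falls on dosing consistency and on the exposure and safety summaries. The 13 and 25 patient design, its type I error and its power are not affected. It should be corrected, but it does not undermine the trial's design.

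**What to change.** Check the text's Grade 2 label against CTCAE v5.0. Then rewrite the hematologic paragraph and the two tables as one rule, in which each cell-count cut-off carries its CTCAE v5.0 grade and each grade has one duration condition and one restart action, stated once. Alternatively, keep both and state which governs. Either way, make clear which lists the 25% restart sentence covers. The sponsor's clinicians must choose the rule; none is proposed here.

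The cost is amendment wording in section 6.1. No change to the sample size or the analysis is needed.

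### Section 6.1 contradicts itself on Grade 4 nausea, diarrhea, neutropenia and thrombocytopenia: after recovery within 14 days the narrative re-doses at 300 mg BID, while the tables stop therapy

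*Combined protocol and SAP*

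**What the plan says.** Section 6.1 of the combined protocol and SAP has two layers: a narrative, then tables for five toxicities.

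- **Narrative, Grade 4.** For "Grade 4 hematologic or non-hematologic" toxicity other than alopecia, or Grade 3 toxicity that persists after one reduction, the action is a cut by a "total of 50 %. BVD-523 dose should not be reduced by more than 50" percent. Discontinuation follows if half dose is not tolerated or recovery is not reached in 14 days. Even then, the PI may keep a patient on a lower dose for clinical benefit.
- **Tables, Grade 4 nausea, diarrhea, neutropenia, thrombocytopenia.** All four say "Off protocol therapy".
- **Narrative, Grade 3 non-hematologic.** If the event resolves within 14 days, "dosing of BVD-523 may be resumed with a 25% dose reduction". Rash is not among the listed exceptions.
- **Rash table.** Grade 3, after a hold: "Resume at same dose level. Oral antibiotics and steroids indicated". Grade 4, after a hold: "Resume at one dose level lower if indicated".
- **Febrile neutropenia.** The narrative lists "grade 3 or 4 febrile neutropenia (defined as temperature" under its Grade 3 hematologic heading, which leads to the 25% reduction. The neutropenia table has no febrile row.

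The narrative's other any-grade carve-out, "Lymphopenia regardless of grade", touches none of these events. Section 5.1 points to Section 6 as a whole. Section 5.5 lists unacceptable adverse events as a reason to stop, without tying them to a grade.

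**The concern.** These are dosing instructions after the most severe non-fatal toxicities. Two sites could treat the same recovered patient in opposite ways, each relying on Section 6.1, and a monitor would have no basis for calling either one a deviation. A site that re-doses at 300 mg BID under the narrative acts against a table row that says to stop.

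Some of these toxicities are foreseeable. Section 7.2 reports rash in two thirds of the first 18 phase 1 patients (12 of 18) and gastrointestinal toxicity at high frequency, in both cases without grades. For neutropenia and thrombocytopenia it gives animal findings only, and in those neutrophils rose.

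**Working it through.** **Inputs.** Starting dose 600 mg BID in 150 mg capsules (Section 5.1); dose levels 0, -1 and -2 = 600, 450 and 300 mg BID (Section 6.1).

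**The plan's own dose levels.** 600 × (1 − 0.25) = 450 mg, or 3 capsules. 600 × (1 − 0.50) = 300 mg, or 2 capsules. Both percentages reproduce the dose-level table, so the narrative's total 50% cut means level -2, from either 600 or 450 mg BID.

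**Main comparison: recovery to baseline or Grade 1 within 14 days**

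| Grade 4 event | On | Narrative | Table |
|---|---|---|---|
| Nausea, diarrhea, neutropenia, thrombocytopenia | 600 mg BID | 300 mg BID (600 mg/day) | off therapy (0) |
| Same | 450 mg BID | 300 mg BID (600 mg/day) | off therapy (0) |

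**Where the two layers generally agree.** If recovery takes more than 14 days, the narrative discontinues, apart from the PI clinical-benefit exception, and the tables have already stopped. A patient already at 300 mg BID who cannot tolerate it also stops under both, with the same exception.

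**Secondary comparisons, from 600 mg BID**

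| Event | Narrative | Table |
|---|---|---|
| Grade 3 rash | may resume at 450 mg BID | resume at 600 mg BID (600/450 = 1.33-fold) |
| Grade 4 rash | 300 mg BID | 450 mg BID (450/300 = 1.5-fold); 600 mg BID (2-fold) only if the row's closing qualifier makes the reduction optional |
| Grade 4 febrile neutropenia | 450 mg BID by its own bullet; 300 mg BID by the general Grade 4 sentence | off therapy, only if the neutropenia itself is Grade 4 |

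Some cells can be reconciled. Grade 4 rash from 450 mg BID gives 300 mg BID under the narrative, and also under the table if the one-level reduction is applied.

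**Design figures.** With 13 + 12 patients, continuing at 2 or more responses and success at 3 or more in total, the probability of success is the sum over k = 2 to 13 of P(X₁ = k) × P(X₂ ≥ 3 − k), with X₁ binomial(13, p) and X₂ binomial(12, p).

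- p = 0.05: 0.0755 (stated 8%).
- p = 0.25: 0.867 (stated 87%).
- Early stopping at p = 0.05, P(X₁ ≤ 1): 0.8646 (stated 0.86).

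These agree with Section 13.2 and do not depend on the dose rules.

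**The case against.** The best defense is that a toxicity-specific table ordinarily overrides a general paragraph. That is a sensible habit of reading, but the documents do not state it. The Grade 4 sentence names its own exception, alopecia, and does not name the four tabulated toxicities. The narrative is not purely general either: it sets its own rules for nausea, diarrhea, thrombocytopenia, neutropenia and febrile neutropenia. Table precedence would also leave the febrile neutropenia bullet and the Grade 4 sentence at odds, since both sit in the narrative. There a reader may reasonably let the named bullet qualify the general sentence, but again nothing says so.

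Other parts of the defense stand and limit the point:

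- A reader might infer that a site cannot follow either layer without breaching the other. That goes too far. A site that stops after a Grade 4 event can rely on Section 5.5.
- The Grade 3 rule is permissive on resuming, so the Grade 3 rash mismatch is softer than two opposed orders.
- A reader might infer that Grade 4 febrile neutropenia always has three answers. The third needs a neutrophil count that is itself Grade 4.
- A reader might take the rash table to be the erroneous layer because its doses are higher. The documents do not support that. The rash table carries the more detailed management plan, and Section 7.2 describes reductions and interruptions as needed in phase 1.
- Immediate notice to the Overall PI of life-threatening complications (Section 5.5), 24-hour SAE reporting (Section 7.4) and DSMC review (Section 12.2) limit harm case by case, but they do not say which rule applies.

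**Conclusion.** The contradiction is real and sits in current text. For four Grade 4 toxicities, in a patient on 600 or 450 mg BID who recovers within 14 days, the narrative gives 600 mg/day and the table gives none, with no order of precedence. The clear conflict arises when a site re-doses under the narrative. The rash and febrile neutropenia mismatches are secondary; the 2-fold rash figure holds on only one reading of the Grade 4 row.

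The frequency cannot be sized. The documents give no Grade 3 or 4 rates for these events and do not reproduce the CTCAE definitions, so all that can be said is that enrollment caps the number at 25 patients. A reader might infer that the trial's error rates or power are compromised; the recomputed figures match those stated, and nothing in the dose rules enters them. The point should be fixed because it concerns patient safety and the repair is cheap. It does not call the design into question.

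**What to change.** Amend Section 6.1 so that each toxicity and grade has one action.

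1. Extend the exception in the narrative Grade 4 sentence to read: *except alopecia and Grade 4 nausea, diarrhea, neutropenia and thrombocytopenia, for which the tables below apply (off protocol therapy)*.
2. State one action for febrile neutropenia, including when the neutrophil count is itself Grade 4. Deleting Grade 4 from the existing bullet is not enough: its count criterion has no lower bound, so an event could still meet both the bullet and the Grade 4 neutropenia row.
3. Have the sponsor choose one rule for Grade 3 and Grade 4 rash, and make narrative and table match. Which rule is a clinical decision that the documents do not settle. If the one-level reduction for Grade 4 is kept, say whether it is mandatory.
4. Once the rows are settled, add: *Where a toxicity and grade has a row in the tables, that row applies; the paragraphs above apply to all other toxicities.*

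Cost: a wording amendment and notification of sites, with no extra visits, patients or data. Patients with the four Grade 4 events lose the option of continuing at 300 mg BID. If the sponsor wants to keep that option, it should change the rows instead and adapt step 1 to match.

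### Section 6.1 gives conflicting Grade 4 instructions: the text reduces the dose to 300 mg BID, four toxicity tables stop therapy, and no sentence says which prevails

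*Combined protocol and SAP*

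**What the plan says.** All the rules below stand in protocol section 6.1.

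- **General text, Grade 4.** For "Grade 4 hematologic or non-hematologic" toxicity (alopecia excepted), and for persistent Grade 3 "toxicity despite one dose level reduction, the dose level will be reduced by a" total of 50%. The text then sets a floor: "BVD-523 dose should not be reduced by more than 50" percent. A patient who cannot tolerate that dose, or whose drug-related toxicity has not resolved within 14 days, is discontinued, "unless clinical benefit has been demonstrated and a lower dose might, in the opinion of the PI, maintain clinical benefit".
- **General text, febrile neutropenia.** Under the Grade 3 hematologic heading, the text lists "grade 3 or 4 febrile neutropenia" as a reason to delay. If the event resolves within 14 days, "dosing of BVD-523 may be resumed with a 25% dose reduction".
- **Nausea, diarrhea, neutropenia and thrombocytopenia tables.** The Grade 4 row of each reads "Off protocol therapy".
- **Rash table.** The Grade 4 row says to hold until Grade 1 or lower, then: "Resume at one dose level lower if indicated".
- **Dose levels.** 600 mg BID (level 0), 450 mg BID (level -1) and 300 mg BID (level -2).

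Section 5.1 refers the reader to Section 6 for dose modifications and sets no order among the rules there.

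**The concern.** An investigator who sees Grade 4 diarrhea in a patient on 600 mg BID finds two written instructions in one section: permanent discontinuation, or continued treatment at 300 mg BID. Following either one departs from the other. If the tables are intended, a site working from the text re-exposes the patient after a Grade 4 event. If the text is intended, a site working from the table ends therapy in a disease for which section 2.1 says there is no effective treatment.

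The tabled toxicities include expected ones. Section 7.2 reports gastrointestinal toxicity at high frequency, and rash in two thirds, among the first 18 patients of the phase 1 study. Those figures are for all grades and give no Grade 4 rate.

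**Working it through.** The check is mainly a comparison of text. The only arithmetic is the dose conversion.

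**Step 1: dose levels.** Starting dose 600 mg BID (section 5.1).
- 25% reduction: 600 × (1 − 0.25) = 450 mg BID.
- 50% reduction: 600 × (1 − 0.50) = 300 mg BID.

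Both match the dose-level table. The Grade 4 sentence does not name 300 mg; the figure follows from its total of 50% and that table.

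**Step 2: general text against the four tables.**

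| Dose at the Grade 4 event | General text | Nausea, diarrhea, neutropenia, thrombocytopenia tables |
|---|---|---|
| 600 mg BID | 300 mg BID | stop |
| 450 mg BID | 300 mg BID | stop |
| 300 mg BID | already at 50%; stop if not tolerated, unless the PI applies the waiver | stop |

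The instructions oppose each other at 600 and 450 mg BID. At 300 mg BID they may coincide, depending on whether the event counts as intolerance and whether the waiver is used.

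**Step 3: rash table, patient on 600 mg BID.** The text gives 300 mg BID. The table gives 450 mg BID if a reduction is judged indicated; if it is not, the row does not exclude resuming at 600 mg BID. Neither outcome is the text's 300 mg BID. At lower doses the comparison depends on that judgement, so no claim is made there.

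**Step 4: febrile neutropenia, patient on 600 mg BID.** The text's febrile neutropenia item names Grade 4 and leads to 450 mg BID. The text's Grade 4 sentence leads to 300 mg BID. This conflict lies within the text. If the neutropenia table is also taken to cover the event, a third answer is to stop; the protocol does not say whether it does.

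**Step 5: search for a precedence rule.** Section 6.1, the pointer in section 5.1 and the removal criteria in section 5.5 contain none. The exception list in 6.1 follows the Grade 3 non-hematologic rule and does not rank text against tables. The only exception written into the Grade 4 sentence is alopecia.

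**Step 6: the waiver.** The text's clinical-benefit waiver does not appear in the table footnotes, which end therapy for delays over two weeks or more than two reductions. Where a patient cannot tolerate 300 mg BID, the waiver also implies a dose below the lowest listed level, despite the 50% floor.

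**The case against.** The strongest reply is that toxicity-specific tables ordinarily override general text. The tables depart from the text at other grades too. Grade 2 nausea is held in the table, whereas the text generally leaves the dose alone at Grades 1 and 2. Grade 3 rash resumes at the same dose in the table but at a 25% reduction under the text. A table that applied only where it agreed with the text would have no purpose.

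That is a reasonable reading and probably the intended one, but it remains an assumption. The text is not confined to toxicities without a table: it sets its own delay rules for thrombocytopenia and neutropenia and its own exceptions for Grade 3 nausea, vomiting and diarrhea. Both sets of rules therefore cover the same events. The convention does not settle whether the neutropenia table covers febrile neutropenia. One can argue that the febrile neutropenia item, being specific, displaces the Grade 4 sentence, but the protocol does not say that either.

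A second reply is that section 5.5 limits the harm. Unacceptable adverse events and the treating investigator's judgement are independent grounds for removal, and life-threatening complications go to the Overall PI immediately. Section 7.4.1 requires serious adverse events to be reported to the Overall PI within 24 hours. This stands as partial mitigation: no site is forced to keep a patient with an unacceptable event on 300 mg BID, and sites do not act unsupervised. None of these provisions says which dose instruction applies.

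**Conclusion.** The conflict is real and the wording should be corrected. For Grade 4 nausea, diarrhea, neutropenia or thrombocytopenia at 600 or 450 mg BID, section 6.1 directs both continuation at 300 mg BID and discontinuation. For Grade 4 rash at 600 mg BID, the table and text differ. For Grade 4 febrile neutropenia at 600 mg BID, the text gives both 450 and 300 mg BID. These results rest on reading the total of 50% as 300 mg BID, which the dose-level table supports, and on the absence of any precedence sentence.

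Three stronger readings are not supported:

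- **That the response rate is biased.** A reader might infer this because stopping and dose reduction change exposure. The documents give no Grade 4 frequency and no link from these rules to response, so neither an effect nor the number of patients affected can be derived.
- **That the rash conflict has a fixed size.** The rash row leaves the reduction to judgement, so the dose difference is not determined.
- **That the stopping limits in text and footnotes otherwise agree.** Fourteen days equals two weeks, but the text can take a patient from 600 to 300 mg BID in one reduction. The footnotes' limit of two reductions therefore need not coincide with the 50% floor.

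**What to change.** Amend section 6.1 as follows:

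1. State that the toxicity-specific tables and their footnotes prevail over the general text, so that Grade 4 nausea, diarrhea, neutropenia or thrombocytopenia ends protocol therapy.
2. Limit the Grade 4 50% sentence and the PI clinical-benefit waiver to toxicities without a table.
3. State one rule for Grade 4 febrile neutropenia and say whether the neutropenia table covers it. If the rule is not a 25% reduction, remove Grade 4 from that list.
4. Have the clinical team confirm the intended dose after Grade 4 rash. Whether it should be 450 mg BID, 300 mg BID or discontinuation is a clinical choice that the documents do not settle.

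The cost is wording in one section of a protocol amendment, with no extra patients, procedures or analyses. The downside is less PI discretion for the tabled toxicities.
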